### 6.5 POOLING OF CENTRES

This section is not applicable because centre/country is not included in any statistical model.

### 6.6 HANDLING OF MISSING DATA AND OUTLIERS

All analyses will be evaluated by observed case analysis (OC), i.e. using only available data without imputation.

Missing or incomplete AE dates are imputed according to BI standards (see “Handling of missing and incomplete AE dates”). (1)

For spirometry endpoints, missing data will not be imputed.

For more details about handling of missing data, see Section 7.5 of CTP.

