3.2 DISCUSSION OF TRIAL DESIGN, INCLUDING THE CHOICE OF CONTROL GROUP

The trial will be conducted as a prospective, open-label design with the objective to collect long term safety data on nintedanib in patients with IPF. The observation period will extend until either every patient is discontinued or a reason for stopping the trial is met (refer to [Section 3.3.4](#)). Patients who have completed one year treatment plus follow-up period in a parent trial are eligible for participation.

The purpose of this trial is to offer the option to all patients who completed the randomized phase III trial 1199.32 or 1199.34 to receive nintedanib treatment if they perceive an individual benefit. The decision to continue treatment will be made by the patient following a discussion with the investigator. The aim of the study is to allow treatment continuation to individual patients; therefore, randomization, blinding and use of placebo would not be appropriate.

To obtain information on the long term safety and tolerability of nintedanib, adverse events and acute IPF exacerbations will be reported, and clinical laboratory tests, electrocardiograms and lung function tests will be performed. FVC derived endpoints will be assessed and data on discontinuations and death will be recorded.

Proprietary confidential information.

© 2017 Boehringer Ingelheim International GmbH or one or more of its affiliated companies. All rights reserved.

This document may not - in full or in part - be passed on, reproduced, published or otherwise used without prior written permission.

The chosen endpoints are a subset of the endpoints used in the parent trial; no new endpoint is introduced in this trial.

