3.3.4 Removal of patients from therapy or assessments

3.3.4.1 Removal of individual patients

The treatment with nintedanib has to be permanently discontinued in the following circumstances:

- Liver function impairment (refer to [Section 10.1](#)):
 - ALT or AST \geq 8 fold ULN.
 - ALT or AST \geq 3 fold ULN for more than 2 weeks despite dose reduction.
 - ALT or AST \geq 3 fold ULN and total bilirubin $>$ 1.5 fold ULN.
 - ALT or AST \geq 3 fold ULN and INR $>$ 1.5.
 - ALT or AST \geq 3 fold ULN with the appearance of fatigue, nausea, vomiting, right upper abdominal quadrant pain or tenderness, fever, rash, and/or eosinophilia ($>$ 5%).
- Diarrhoea: reoccurrence of diarrhoea ($>$ 4 stools/day) for 8 or more consecutive days despite dose reduction and supportive care as described in [Section 4.2.1.1](#).
- Pregnancy (refer to [Section 5.3.7](#)).
- Planned usage of a specific investigational drug (refer to [Section 4.2.2.1](#)).
- Treatment interruption. Treatment interruption is acceptable in certain cases and for a defined period which are described in [Section 4.2.1](#).

Similar to the parent study, in the following cases withdrawal of study drug is highly recommended. Only in special circumstances, the investigator, upon thorough assessment of all available clinical data, and taking into consideration the potential risks associated with administration of nintedanib, may decide not to withdraw the patient, even though one or more of the below mentioned criteria are fulfilled. However, in such a case, continuation of study treatment should be discussed with the patient, and the decision documented in the source data.

Proprietary confidential information.

© 2017 Boehringer Ingelheim International GmbH or one or more of its affiliated companies. All rights reserved.

This document may not - in full or in part - be passed on, reproduced, published or otherwise used without prior written permission.

- Planned major surgery, including any major abdominal or intestinal surgery.
- Patients who require full-dose therapeutic anticoagulation (e.g. vitamin K antagonists, dabigatran, heparin, hirudin), or high-dose antiplatelet therapy.
- Major thrombo-embolic events e.g. stroke, deep vein thrombosis, pulmonary embolism, myocardial infarction.
- Increased risk of bleeding e.g. haemorrhagic CNS event, gross / frank haemoptysis or haematuria, active gastro-intestinal bleeding or ulcers.

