- Deterioration of the disease. A ≥ 10 % decrease in the absolute value of FVC% predicted within 12 months is considered deterioration (progression of disease).

Patients have the right to withdraw from the study at any time without the need to justify the decision. The investigator has the right to remove patients from the study for non-compliance, administrative or other reasons.

Data of patients who discontinue or withdraw prior to medication assignment will be recorded in the eCRF. Data of patients who discontinue or withdraw after medication assignment must be documented and the reason for withdrawal must be recorded in the eCRF. The data must be included in the trial database and must be reported.

Refer to [Section 6.2.2](#) and [Section 6.2.3](#) for procedures to be followed for patients terminating the trial.

Patients who are discontinued from this trial are not allowed to be re-enrolled.

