7. STATISTICAL METHODS AND DETERMINATION OF SAMPLE SIZE

7.1 STATISTICAL DESIGN - MODEL

This is a multicenter, multi-national, open-label clinical trial to investigate the long term safety of nintedanib in patients with IPF previously treated in a double-blind phase III placebo controlled trial (1199.32 or 1199.34).

This statistical paragraph deals with the analyses to be performed on the extension trial only. Although data of parent trial will not be described in the scope of these analyses, they will be taken into account for adverse events analyses, as described in [Section 7.3.4](#).

As the main objective of this extension trial is to study long-term safety, only descriptive statistics will be used.

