7.5 HANDLING OF MISSING DATA

Missing or incomplete AE dates will be imputed according to BI rules. No imputation is planned for other safety criteria.

Proprietary confidential information.

© 2017 Boehringer Ingelheim International GmbH or one or more of its affiliated companies. All rights reserved.

This document may not - in full or in part - be passed on, reproduced, published or otherwise used without prior written permission.

Missing or incomplete data for survival are managed by censored data analyses. No specific procedures need to be specified to handle them.

For spirometry endpoints, missing data will not be imputed.

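### By-visit observed-case FVC means will lean towards stability, because stopping drug is strongly advised after a large FVC fall and FVC collection then ends

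*SAP*

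**What the plan says.** **Analysis.** Protocol 3.2 announces that "FVC derived endpoints will be assessed and data on discontinuations and death will be recorded". Protocol 7.1 adds that "As the main objective of this extension trial is to study long-term safety, only descriptive statistics will be used". On missing values SAP 6.6 states "All analyses will be evaluated by observed case analysis (OC), i.e. using only available data without imputation", and Protocol 7.5 says "For spirometry endpoints, missing data will not be imputed". SAP 6.7 assigns spirometry to visit windows at weeks 64 and 80 and every 16 weeks after that, and bases the statistical tables on those re-calculated visits. SAP 7 lists N, mean, SD, minimum, median and maximum as the summary statistics. SAP 6.3 runs everything on the Treated Set, with the total column of main interest.

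**Withdrawal.** Protocol 3.3.4.1 says that "in the following cases withdrawal of study drug is highly recommended". One of the cases is deterioration, worded as "A ≥ 10 % decrease in the absolute value of FVC% predicted within 12 months is considered deterioration (progression of disease" (closing bracket cut). The rule leaves discretion: in special circumstances the investigator "may decide not to withdraw the patient, even though one or more of the below mentioned criteria are fulfilled", after discussion with the patient and with the decision documented.

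**End of FVC collection.** The flow chart shows spirometry at the end-of-treatment visit and at the follow-up visit 28 days after last intake, and none later.

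**The concern.** Withdrawal depends partly on the variable being summarised. A patient whose FVC falls fast contributes the value that met the criterion, an end-of-treatment value and a follow-up value, and is then absent from every later visit. A by-visit mean at week 96 or week 192 describes those who stayed, yet it stands under an all-treated heading.

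The trial has no comparator and is expected to last about 6½ years, so nothing in the design would reveal an artificial flattening of the curve. Protocol 2.3 describes the benefit of the drug as slower FVC decline. A flattening mean curve could therefore be read as sustained benefit when part of it comes from who remained.

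**Working it through.** The plan gives no sample size, power or FVC projection, so there is no figure of its own to reproduce. Direction follows from the text; size needs assumptions.

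**Inputs from the documents (Protocol 1.2).** The nintedanib slopes in the two parent trials were −114.65 and −113.59 mL/year, mean (114.65 + 113.59)/2 = 114.1 mL/year of decline. The slope differences were 125.26 (77.68 to 172.84) with 515 randomised and 93.73 (44.78 to 142.68) with 551 randomised.

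**Rough bound on slope spread.** SE = CI width/(2 × 1.96): 95.16/3.92 = 24.28 and 97.90/3.92 = 24.97. If allocation was 1:1 (not stated), SD = SE × √(N/4): 24.28 × √(515/4) ≈ 275 and 24.97 × √(551/4) ≈ 293 mL/year. With 3:2 allocation the values are about 270 and 287. These include measurement error, so 150–250 mL/year for true slopes is a reasonable working range.

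**First simulation.** 40,000 patients with linear FVC on the flow-chart visits.
- Withdrawal: a fall of at least 10 points of FVC % predicted from the earliest visit in the preceding 12 months makes a patient eligible, and an assumed share of such patients then leaves. The visit showing the fall stays in the data.
- Other assumptions: visit SD 80–100 mL, predicted FVC 3.0–4.0 L, FVC-independent dropout 0.15 per year.
- Understatement = 1 − (observed-case mean ÷ mean if nobody left).

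Week 96, mean change in mL:

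| Slope SD / visit SD / predicted FVC | Nobody leaves | 25% withdrawn | 50% withdrawn |
|---|---|---|---|
| 150 / 80 / 4.0 L | −214 | −203 (5%) | −188 (12%) |
| 150 / 80 / 3.5 L | −214 | −197 (8%) | −177 (17%) |
| 200 / 100 / 3.5 L | −215 | −184 (14%) | −147 (32%) |
| 250 / 80 / 3.5 L | −216 | −177 (18%) | −130 (40%) |
| 250 / 80 / 3.0 L | −216 | −172 (20%) | −116 (46%) |

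Example: 1 − 147/215 = 32%. In the 200 / 100 / 3.5 L case at week 192 the means are −429 (nobody leaves), −359 (16%) and −259 (40%). With no FVC-driven withdrawal the observed-case mean stayed within about 7 mL of the full mean in every setting, so the withdrawal rule causes the gap.

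**Second simulation.** 6,000 patients per scenario, slope SD 150–250 mL/year, visit SD 100 mL, predicted FVC 3.5 L, other dropout 10% per year. Understatement:

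| Week | 25% withdrawn | 50% withdrawn |
|---|---|---|
| 48 | 6–13% | 11–25% |
| 96 | 10–21% | 22–46% |
| 192 | 13–24% | 30–52% |

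The summary range of roughly 10–45% at week 96 comes from this run. Letting predicted FVC vary from 3.0 to 4.0 L, as in the first run, lowers the bottom end to about 5%.

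**Model on the same data.** In the second simulation a random intercept and slope model fitted to the observed values only came within 3 mL/year of the true slope in all six scenarios (slope SD 200, 50% withdrawn: −116 against −119 mL/year). This is close to built in, because the simulated data were linear and FVC-related dropout depended only on observed FVC.

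**The case against.** The strongest reply is that the FVC analysis itself cannot be seen. The protocol and SAP sections defining and analysing these endpoints are not public, and no visible sentence plans mean FVC change by visit. That reading comes from the windowing rule, the list of summary statistics and the descriptive-only statement. Protocol 3.2 says the endpoints are a subset of those in the parent trials. The parent primary endpoint was an annual rate of FVC decline, reported as an adjusted rate, so a modelled slope may already be planned. SAP 6.6 would permit it, since such a model uses available data without imputation. All of this stands.

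Some safeguards are also visible: N is shown with each summary, SAP 7.7 gives Kaplan-Meier plots of treatment discontinuation, and SAP 6.6.1 covers time to death. They show that patients leave, but not how leaving relates to FVC.

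Three stronger readings are tempting, and the documents do not support them:
- *Observed-case means are the only FVC result.* The non-public sections leave this open.
- *Those who stay have not declined.* The rule is a recommendation with discretion, needs a fall of 10 or more within 12 months, and leaves slower decliners in. The selection is against fast decline.
- *The percentages forecast this trial's bias.* They depend mainly on how often the recommendation is followed, which is assumed.

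The stakes are limited: the primary endpoint is adverse-event incidence, there are no secondary endpoints, and Protocol 7.2 foresees no formal inference. On-treatment values are a legitimate description of patients still on drug, provided they are labelled as such.

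**Conclusion.** The point holds for by-visit means under the visible rules: later mean FVC changes will lean towards stability, and more so with time. A slope model in the non-public sections would largely protect that output but would not remove the lean from the by-visit means.

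The size cannot be derived from the documents. With 25–50% adherence to the recommendation and slope SD 150–250 mL/year, decline at week 96 is understated by roughly 10–45%; the other assumptions move the lower end. Deaths and other disease-related dropout were not modelled as depending on FVC and would probably add bias in the same direction.

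This affects how a descriptive result is read. It does not affect the primary safety endpoint. The change is worth making because nothing in an uncontrolled trial would correct the impression.

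**What to change.** In SAP 6.6 and the FVC analysis section:

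1. Label by-visit observed-case FVC means as describing *patients still on treatment*.
2. Show the same means by time of last FVC, for example before week 48, weeks 48–96, and later.
3. Base any statement on long-term FVC course on an annual rate of change, with estimate and 95% CI and no test. Take it from a random intercept and slope model fitted to all on-treatment FVC values of Treated Set patients, up to and including end of treatment, at the actual measurement day.

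If the non-public section already holds such a model, only items 1 and 2 are needed. The withdrawal criterion is not affected.

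**Cost.** SAP wording, one extra table and at most one model, all on data already collected. The model assumes approximate linearity and dropout that depends on observed FVC. Deaths and acute exacerbations may violate the second assumption, and the report should say so. An estimate with an interval also slightly relaxes the descriptive-only wording of Protocol 7.1, so the SAP should record that under changes to the planned analysis.

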### 6.6.1 Time to event endpoints

Missing data for time-to-event endpoints are managed by censored data analyses. No specific procedures need to be specified to handle them.

If a patient has no event during the studied period then he will be censored on the day corresponding to the end date of the studied period. The studied period for each type of endpoint is detailed in [Table 6.6.1: 1](#).

Table 6.6.1: 1                      Censoring rules for time to event endpoints

Endpoint	Studied period	Censoring rule
Time to death Time to first IPF acute exacerbation	From first trial drug intake in 1199.33 to last contact date	Patients with no event at the cut-off date will be censored at their last contact date
Time to first dose reduction Time to first treatment interruption Time to permanent treatment discontinuation	From first trial drug intake in 1199.33 to last trial drug intake	Patients with no event at the cut-off date will be censored at their last trial drug intake
Time to first occurrence of adverse event of particular note Time to first liver enzyme elevation	From first trial drug intake in 1199.33 to last trial drug intake + 28 days	Patients with no event at the cut-off date will be censored at their last trial drug intake + 28 days

Cut-off date = Date of the interim database lock

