© 2017 Boehringer Ingelheim International GmbH or one or more of its affiliated companies. All rights reserved.

This document may not - in full or in part - be passed on, reproduced, published or otherwise used without prior written permission.

Time to first acute IPF exacerbation over 52 weeks was a key secondary endpoint in the studies. In study 1199.32 there was no difference between the treatment groups and the hazard ratio (HR) was 1.15 (95% CI: 0.54, 2.42; p=0.673). In study 1199.34 the risk of having a first acute IPF exacerbation was significantly lower in the nintedanib group than in the placebo group, with a HR of 0.38 (95% CI: 0.19, 0.77; p=0.005).

In both studies, survival endpoints showed a consistent numerical difference in favour of nintedanib. The HR for time to death over 52 weeks in a pre-specified pooled analysis of both studies was 0.70 (95% CI 0.43, 1.12; p = 0.1399).

As expected, the most frequent AEs were gastrointestinal disorders. Diarrhoea was reported in 61.5% of the patients in the nintedanib group in study 1199.32 and in 63.2% of the patients in study 1199.34 compared to 18.6% and 18.3% in the placebo group, respectively. Liver enzyme elevations were more frequent in the nintedanib group than in the placebo group in both studies: aspartate aminotransferase [AST] and/or alanine aminotransferase [ALT] ≥ 3 xULN was observed in 4.9% of the patients in the nintedanib group versus 0.5% of the patients in the placebo group in study 1199.32 and in 5.2% of the patients in the nintedanib group versus 0.9% of the patients in the placebo group in study 1199.34. There was no Hy's law case in the nintedanib group.

Please refer to the current version of the Investigator's Brochure ([U07-1248](#)) for complete and updated information on nintedanib in IPF.

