6.2.2 Treatment period

If the patient has been determined eligible by the investigator to enter the trial (refer to [Section 3.3](#)), the investigator will assign a medication number to the patient through IVRS/IWRS at Visit 2 (refer to [Section 4.1.2](#)). First dose of nintedanib will be administered at Visit 2 in the clinic (day 1).

Additional clinic visits will be scheduled after 2, 4, 6, 12, 24, 36 and 48 weeks of treatment (Visits 3-9). Liver function monitoring visits will be performed at 18, 30 and 42 weeks of treatment (Visits 6a, 7a and 8a). After the first year of treatment, complete clinic visits will be scheduled every 16 weeks with intermediate liver function monitoring visits.

For detailed description of the trial procedures at each visit and dispensing schedule, please refer to the [Flow Chart](#).

End of Treatment (EOT)

If a reason for drug discontinuation is met (refer to [Section 3.3.4](#)) an EOT Visit should be scheduled as soon as possible after last drug intake. Reason for discontinuation must be documented in the eCRF.

For detailed description of the trial procedures at the EOT visit, please refer to the Flow Chart.

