## **6. GENERAL ANALYSIS DEFINITIONS**

### **6.1 TREATMENT(S)**

For treatment specifications, see Section 4 of CTP.

The following periods of interest will be defined: previous trial, between trials, screening, off-treatment, treatment period, post-treatment, follow-up and post-study as follows:

Note: the last day of each of the following periods is excluded.

- Previous trial: from screening in parent trial to the last trial drug intake in parent trial plus 28 days plus one day / or to the date of trial completion in parent trial plus one day / or to date of informed consent in 1199.33, whichever occurs later
- Between-trials: from end of previous trial period (see above) to date of informed consent in 1199.33
- Screening: from date of informed consent in 1199.33 to first trial drug intake in 1199.33
- Treatment period: from first trial drug intake in 1199.33 (or re-start of treatment if interruption) to last trial drug intake (or date of interruption if interruption) plus one day
- Off-treatment: from date of start of interruption to re-start of treatment
- Post-treatment: from the last trial drug intake plus one day to last trial drug intake plus 28 days plus one day
- Follow-up: from last trial drug intake plus 28 days + one day (after post-treatment period) to date of trial completion plus one day. This period is only created if last trial drug intake took place more than 28 days before trial completion.
- Post-study: from the last trial drug intake plus 28 days plus one day to database lock or from the date of trial completion (after follow-up period) plus one day to database lock, whichever occurs later

Most treatment periods are optional (e.g. “Between-trials”, “Screening” and “Follow-up” will not concern all the patients).

For safety analyses ([Section 7.8](#)), data from first trial drug intake in 1199.33 up to 28 days after last trial drug intake (included) will be considered as on-treatment period.

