The frequency of patients with adverse events will be summarised by randomised treatment in parent trial, primary system organ class and preferred term. Separate tables will be provided for patients with other significant adverse events according to ICH E3 (3), for

patients with serious adverse events, for patients with adverse events occurring with an incidence in preferred term greater than 5% (in at least one treatment arm), for patients with protocol specified significant adverse events (as ticked in the AE page of the CRF), for patients with related adverse events, for patients with adverse events leading to dose reduction and for patients with adverse events leading to treatment discontinuation.

The system organ classes will be sorted according to the standard sort order specified by EMA, preferred terms will be sorted by descending frequency over the total column (within system organ class).

Specific tables will be created in order to describe selected adverse events of particular note, such as diarrhoea events:

- Display of the diarrhoea specific page of the CRF
- Summary of diarrhoea events including time to onset, number and duration of episodes
- Summary of diarrhoea adverse events including seriousness, clinical consequences (dose -reduction, drug discontinuation or drug interruption) and outcome
- Kaplan-Meier plots of time to first diarrhoea event, by randomised treatment in parent trial and overall

Specific summary tables including seriousness, clinical consequences and outcome will also be presented to describe the following adverse events of particular note: nausea, vomiting, dehydration and weight decrease adverse events. Depending on the number of patients having such adverse events, summary tables including time to onset, number of episodes and duration together with Kaplan-Meier plots of time to first event, by randomised treatment in parent trial and overall, may also be produced with and without a y-axis cut-off at 70%.

Topics or syndromes that are medically relevant to the clinical development program are specified in [Table 7.8.1: 1](#). The frequency of patients with AEs within these topics or syndromes will be summarised by treatment, topic or syndrome and preferred term. A separate table will be provided for patients with serious AEs (SAEs), by treatment, topic or syndrome and preferred term.

Table 7.8.1:1 Aggregated adverse events by topic or syndrome

Organ system	Topic or Syndrome	Term selection

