## 7.8.2 Laboratory data

The analyses of laboratory data will be descriptive in nature and will be based on BI standards (4).

Specific tables will be presented to describe liver enzyme elevations as defined in [Section](#)

5.4.4:

- Summary table of liver enzyme elevation including time to first onset and number of episodes
- Kaplan-Meier plot of time to first liver enzyme elevation (if sufficient number of events). No statistical test will be performed.
- Summary table of individual maximum liver enzyme and bilirubin elevations
- Plot of timecourse profile of liver enzyme for patients having liver enzyme and bilirubin elevation

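### SAP Table 6.6.1:1 censors first AE of particular note and first liver enzyme elevation at last intake + 28 days, with no visible stop at death, last contact or data cut-off

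*SAP*

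**What the plan says.** SAP 6.6.1 gives a general rule for a patient without an event: "he will be censored on the day corresponding to the end date of the studied period". Table 6.6.1:1 then sets a studied period for each endpoint.

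- **Death and first acute exacerbation:** censored at last contact.
- **Dose reduction, interruption and discontinuation:** censored at last intake.
- **First AE of particular note and first liver enzyme elevation:** the period runs to 28 days after last intake, and "Patients with no event at the cut-off date will be censored at their last trial drug intake + 28 days".

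The footnote reads "Cut-off date = Date of the interim database lock". In the rule, the cut-off decides who counts as event-free. It does not limit the censoring date.

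The 28 days come from the safety window in SAP 6.1: "data from first trial drug intake in 1199.33 up to 28 days after last trial drug intake (included) will be considered as on-treatment period". That window has no stop at death, last contact or lock either.

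The rule feeds these outputs:

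- SAP 7.8.1 plans "Kaplan-Meier plots of time to first diarrhoea event, by randomised treatment in parent trial and overall" without condition. Plots for nausea, vomiting, dehydration and weight decrease depend on patient numbers.
- SAP 7.8.2 plans a "Kaplan-Meier plot of time to first liver enzyme elevation (if sufficient number of events"), also conditional.

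**The concern.** A censoring date should be no later than the last day on which an event could have been recorded. Last intake + 28 days meets this for a patient who is alive and followed for the full 28 days, which is what the Follow-up Visit is for. It fails for three groups:

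1. patients who die on drug or within 28 days of last intake;
2. patients lost, or withdrawing consent, within those 28 days (Protocol 3.1 recognises that such patients may not reach the Follow-up Visit);
3. patients on drug, or less than 28 days past last intake, at the lock. Protocol 6.2.5 expects some patients to continue treatment after the final-analysis lock.

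The added days enlarge the risk sets and cannot contribute events, so each Kaplan-Meier step is too small. At stake is the accuracy of descriptive toxicity curves in a trial whose only objective is long-term safety.

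**Working it through.** The documents give no curve value or event count to reproduce, so the check compares the literal rule with the capped rule.

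**Inputs from the documents**
- Diarrhoea: "Diarrhoea was reported in 61.5% of the patients in the nintedanib group in study 1199.32 and in 63.2% of the patients in study 1199.34" over 52 weeks (Protocol 1.2). As a constant hazard: −ln(1 − 0.615) = 0.955 and −ln(1 − 0.632) = 1.000 per year.
- AST/ALT at least 3 × ULN: 4.9% and 5.2% over 52 weeks (Protocol 1.2), giving 0.0502 and 0.0534 per year.
- Follow-up at the final lock: the parent reports are dated 7 and 8 April 2014 (Protocol 9.2), so parent Visit 9 came earlier. Visit 2 is due within 12 weeks of Visit 9, so last entry was by 8 April + 84 days = 1 July 2014. If the lock is not before the SAP date of 25 July 2017, minimum potential follow-up is 3.07 years.

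**Assumed:** constant hazards; death μ = 0.05–0.08 per year; stopping 0.15–0.25 per year; hazard λ of other AEs 0.05–0.20 per year.

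**Effect of deaths.** Each event-free death on drug adds h = 28/365.25 = 0.0767 year. Added time as a fraction of true time at risk is about μh, so the estimated hazard becomes λ/(1 + μh):
- μ = 0.05: μh = 0.00383, hazard 0.38% too low;
- μ = 0.08: μh = 0.00613, hazard 0.61% too low.

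The drop in 1 − KM at time t is about λt · exp(−λt) · μh:

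| Endpoint | λ | t (years) | μ | Drop (points) |
|---|---|---|---|---|
| Other AE | 0.05 | 3 | 0.05 | 0.15 × 0.861 × 0.383 = 0.05 |
| Other AE | 0.20 | 3 | 0.08 | 0.60 × 0.549 × 0.613 = 0.20 |
| Diarrhoea | 0.955 | 1 | 0.05 | 0.955 × 0.385 × 0.383 = 0.14 |
| Diarrhoea | 1.000 | 1 | 0.08 | 1.000 × 0.368 × 0.613 = 0.23 |
| Liver | 0.0502 | 3 | 0.05 | 0.151 × 0.860 × 0.383 = 0.05 |
| Liver | 0.0534 | 3 | 0.08 | 0.160 × 0.852 × 0.613 = 0.08 |

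Simulation with 400,000 patients per scenario gives the same figures.

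**Effect of the lock.** At the final lock, time added for ongoing patients falls after year 3.07, so the curve up to year 3 does not change. The overall event rate (events per person-time) does:
- other AEs: 0.7–1.8% too low if ongoing patients are on drug at the lock, 0.4–0.6% if all stopped at least 28 days before it;
- diarrhoea: 0.4–0.7% too low.

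For a lock 48 weeks after last entry (the second interim in Protocol 7.4), the AE rate is 2.5–4.8% too low and the diarrhoea rate 1.4–2.7%, with at most 0.35 points on the 1-year diarrhoea curve.

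**Wider assumptions.** Take death 0.08–0.35 per year (upper end guided by the 2–3 year life expectancy in Protocol 1.1), stopping 0.15–0.47 per year (upper end from 37.6% in phase II: −ln(1 − 0.376) = 0.47), and 0–100% of stoppers unobserved after last intake. The 1-year diarrhoea gap is then 0.2–2.3 points by simulation. The formula agrees at the extreme: (0.35 + 0.47) × 0.0767 = 0.0629; a hazard of 0.968 (62% at 1 year) becomes 0.910, and 62.0% becomes 59.8%. At an interim lock the far right of the curve can be about 2.4 points low.

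**The case against.** **The direction depends on the comparator.** A reader might infer that these curves understate the share of patients who actually have the event. The documents do not support that. The statement here is relative to a Kaplan-Meier estimate censored at death, last contact or lock. Such an estimate itself exceeds the proportion affected, because patients who die first cannot have the event. With μ = 0.05–0.08, 1 − KM exceeds that proportion by 1.0–4.5 points for other AEs at 3 years and 1.3–2.1 points for diarrhoea at 1 year, far more than the missing cap removes. The SAP also does not say whether event or event-free probability is plotted. This objection stands, and the comparator has to be named.

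**The cap may exist in text not shown.** SAP 5.4.3, 5.4.4 and 9.2 are cited but withheld, and the visible text does not say how last intake is set for a patient still on drug at a lock. SAP 6.6 limits analyses to available data, which suggests the intent but sets no date. This also stands, so the finding is about the visible table.

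**The effect is small and rests on assumptions.** With about 750 patients, the standard error is about √(0.62 × 0.38/750) = 1.8 points at 62% and √(0.14 × 0.86/750) = 1.3 points at 14%, several times the final-lock shift. The parent-trial rates may not apply to a population of 52-week completers. This supports a minor rating but does not make the written rule right.

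**Conclusion.** The point holds as a minor error in a stated rule. Followed literally, Table 6.6.1:1 counts unobservable days as time at risk. Cumulative incidence then reads about 0.05–0.25 points below the properly capped Kaplan-Meier estimate at the final lock, and more at an interim lock or where patients are lost soon after stopping. The sizes rest on assumed death and stopping rates and constant hazards; the direction against that comparator does not.

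A reader might draw two further inferences that the documents do not support:

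- **That the primary safety result is affected.** It is a number and percentage of patients (Protocol 5.1.1) and does not use this rule. No test or decision depends on the curves.
- **That liver enzymes must be censored at the last sample.** The flow chart schedules no laboratory test after the EOT visit, and "an EOT Visit should be scheduled as soon as possible after last drug intake", so most of the 28 days has no scheduled sample. But the EOT sample, the retests in Protocol 4.2.1.2 and the follow-up of abnormal results in Protocol 6.2.3 can fall inside it. Liver status between any two scheduled samples is also unobserved. Censoring at the last sample is one convention among several.

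**What to change.** In Table 6.6.1:1, replace the rule shared by the two endpoints with: *censored at the earliest of last trial drug intake + 28 days, death, last contact and data cut-off*. If a withheld section already contains this cap, add a cross-reference instead.

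Optionally, for liver enzyme elevation, state whether censoring is at that date or at the last liver sample on or before it.

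The cost is one line of SAP text and a minimum over dates already collected in the program that sets the censoring date. No new data are needed and the primary tables do not change.
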